8.4.3 Exclusion Criteria

Subjects will be excluded from the study if 1 or more of the following criteria are applicable at the Screening Visit:

1. Premature (gestational age less than 37 weeks) AND < 1 year of post-natal age.
2. Known to have significant comorbidities, including genetic disorders (eg, trisomy 21); cardiopulmonary diseases (eg, haemodynamically significant congenital heart disease); significant pulmonary disease (eg, bronchopulmonary dysplasia, cystic fibrosis); history of surgery for diaphragmatic hernia; any hereditary or acquired metabolic diseases, haematological or other malignancy; or is known to be HIV positive; or has evidence of severe neurologic impairment or developmental delay that would limit the ability to administer study drug or evaluate the safety or clinical response to IMP.
3. Current respiratory insufficiency likely to require imminent invasive mechanical ventilation (Part C only).
4. Malformation of the gastrointestinal tract including unresolved pyloric stenosis, history of necrotising enterocolitis, short bowel, or other significant condition that would alter drug absorption or increase the risk of diarrhoea.
5. Any clinically significant electrocardiogram (ECG) abnormalities.
6. Known to be immunocompromised.
7. High probability of asthma (per [GINA Guidance 2020](#)) with all of the following:
 - a. Symptoms (cough, wheeze, heavy breathing) for > 10 days during previous upper respiratory infections
 - b. History of > 3 episodes per year or severe episodes and/or night worsening
 - c. Between episodes, child has cough, wheeze, or heavy breathing during play or when laughing
 - d. Allergic sensitisation, atopic dermatitis, food allergy, or family history of asthma
8. Suspected of having a clinically significant bacterial infection, as indicated by symptoms or laboratory findings consistent with a bacterial infection, including but not limited to: elevated white blood cell count, elevated C-reactive protein, chest X-ray consistent with bacterial pneumonia, unstable vital signs, hypotension, or evidence of shock or poor perfusion.
9. Has significant oral and/or maxillofacial malformations that would limit the ability to administer IMP.
10. History of renal failure including renal anomalies likely to be associated with renal insufficiency (eg, clinical conditions of renal dysplasia, polycystic renal disease, renal agenesis).
11. Clinical evidence of hepatic decompensation (eg, hepatic disorder with associated coagulopathy or associated encephalopathy) or significantly elevated liver enzymes

(aspartate aminotransferase [AST] and/or alanine aminotransferase [ALT] > 3 × the upper limit of normal).

12. History of epilepsy or seizures. Subjects with a history of febrile seizures will be permitted to enrol.
13. Allergy to test medication or constituents.
14. Known to be concurrently infected with COVID-19 virus (SARS-CoV-2).
15. Requires any prohibited medication/therapy during the course of the study:
 - a. Requires inhaled, oral, or IV corticosteroids therapy during the dosing period of the study.
 - b. Has taken within 21 days before dosing, or requires during the dosing period of the study, any drug that could impact on the PK of the investigational product including potent inhibitors or potent and moderate inducers of CYP P450s (as listed in [Appendix 17.3](#)).
 - c. Has taken within 21 days before dosing, or requires during the dosing period of the study, any prescription medications, over-the-counter (OTC) medications, herbal remedies or dietary supplements containing CCI or the consumption of CCI-containing products.
 - d. Requires the use of Heliox, leukotriene receptor antagonist (eg, montelukast), exogenous surfactant, or mucolytics during the dosing period of the study.
16. Has received 1 or more doses of palivizumab at any time before Screening or received treatment with antiviral therapy for RSV (eg, ribavirin or intravenous [IV] immunoglobulin) within 3 months before the Screening Visit. **Note:** Subjects eligible for palivizumab treatment or other RSV prophylaxis cannot be included in the study.
17. The subject's parent(s) or legal guardian(s) is a study team member (ie, has direct involvement in this study or other studies under the direction of the Investigator or the study centre) or is a family member of either the Investigator or other team members.
18. Currently participating in any investigational study or at the time of screening, has received an investigational product within 3 months or within 5 half-lives of the investigational product, whichever is longer.
19. Any other reason which in the opinion of the Investigator makes the participant unsuitable for a clinical trial.

8.4.4 Removal of Subjects from Therapy or Assessments

Subjects may be withdrawn from the study for any of the following reasons:

- Parent/legal guardian request
- Use of prohibited concomitant medication/therapy

- Non-compliance with the protocol
- Lost to follow-up
- Occurrence of AEs that are not compatible with the continuation of the subject in the study, in the Investigator's opinion, or that make it unacceptable to the subject's parent/legal guardian for them to continue
- Investigator request
- Intercurrent illness
- Sponsor request
- Becoming critically ill with respiratory insufficiency leading to the requirement for mechanical ventilation/positive airway pressure (PAP)/high-flow oxygen
- Randomisation code broken prematurely (Parts B and C)

Parents/legal guardians are free to withdraw their children from the study at any time without providing reason(s) for withdrawal and without prejudice for receiving further treatment. The reason(s) for withdrawal will be documented in the case report form (CRF). Parents/legal guardians who choose to withdraw their child from the study will be encouraged to allow their child to complete the same final evaluations as subjects completing the study according to the protocol, particularly safety evaluations.

All reasonable efforts should be made to contact the parent/legal guardian of a subject who is lost to follow-up. These efforts must be documented in the subject's file.

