8.5.6.1 Permitted Medication/Therapy

RV521 is a weak inhibitor of MATE-1. Metformin should be used with caution and glucose levels should be closely monitored.

Medications that are CCI substrates with a narrow therapeutic range (See Appendix 17.3) such as fentanyl that are required, e.g. in patients requiring procedures or ventilation, will be permitted provided that the subjects are appropriately monitored by the investigator who should be aware that the active investigational product (sisunatovir) may compete for the metabolism of such products, resulting in higher drug levels of these medications.

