8.5.6.2 Prohibited Medication/Therapy

The following medications/therapy will not be permitted during the study:

- Palivizumab or treatment with any antiviral therapy for RSV (eg, ribavirin or IV immunoglobulin)
- Corticosteroids (oral, IV, or inhaled)
- Heliox
- Leukotriene receptor antagonists (eg, montelukast)
- Exogenous surfactant
- Mucolytics
- Any drug, which could impact on the PK of the investigational product including potent inhibitors or moderate or potent inducers of CYP P450s (for details see Appendix 17.3).
- Herbal preparations/medications are not allowed throughout the study. These herbal medications include, but are not limited to CCI, kava, ephedra (ma huang), ginkgo biloba, dehydroepiandrosterone (DHEA), yohimbe, saw palmetto, and ginseng.
- Consumption of CCI-containing products are not allowed throughout the study. CCI.

Subjects who need to start treatment with prohibited medications during the study will be required to discontinue study treatment, but must remain in the study according to the post-study drug treatment period specified in the Schedule of Assessments, and should also attend the follow-up visit. After the end of their participation in the study, each subject will be treated according to standard clinical practice.

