9.4.5 Post Treatment (Part C)

Visit Day 7 (40 – 48 Hours Post-Dose 10) Follow-up:

Note: Visit Day 7 may occur on Study Days 7 or 8 depending on when the subject received his or her first dose of IMP.

- Physical examination
- Evaluation of hydration status
- Body weight/length/head circumference
- Vital signs (body temperature, systolic and diastolic BP, HR, RR)
- 12-Lead ECG
- Record RSV-related signs and symptoms, and severity (if indicated), including: temperature, cough, coryza, grunting with expiration, nasal flaring, retractions, and wheezing
- ReSVinet scale for clinicians ([Appendix 17.6](#))
- Adapted ReSVinet Scale for Parental use ([Appendix 17.2](#))
- Safety laboratory tests (clinical chemistry and haematology)
- Urinalysis
- PK blood sample according to sampling schedule in [Table 5](#)
- Nasopharyngeal swab
- Concomitant medication review
- Adverse event review

Visit Day 14 Follow-up:

- Vital signs
- Body weight/length/head circumference
- Record RSV-related signs and symptoms, and severity (if indicated), including: temperature, cough, coryza, grunting with expiration, nasal flaring, retractions, and wheezing
- ReSVinet scale for clinicians ([Appendix 17.6](#))
- Adapted ReSVinet scale for parental use ([Appendix 17.2](#))
- Nasopharyngeal swab
- Concomitant medication review
- Adverse event review

Visit Day 34 Follow-up:

- Vital signs
- Body weight/length/head circumference
- Record RSV-related signs and symptoms, and severity (if indicated), including: temperature, cough, coryza, grunting with expiration, nasal flaring, retractions, and wheezing

- ReSVinet scale for clinicians ([Appendix 17.6](#))
- Adapted ReSVinet scale for parental use ([Appendix 17.2](#))
- Nasopharyngeal swab
- Concomitant medication review
- Adverse event review

Early Withdrawal (or Discontinuation) Visit

Parents/legal guardians who withdraw their child from the study will be encouraged to allow their child to complete the same final evaluations as subjects completing the study according to this protocol (ie, at the relevant post-treatment visit), particularly safety evaluations.

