10.1.3.1 Adverse Events

Adverse Event Definition

An AE is defined as any untoward medical occurrence in a clinical study subject administered a medicinal product which does not necessarily have a causal relationship with this treatment. An AE can therefore be any unfavourable and unintended sign (including an abnormal laboratory finding), symptom, or disease temporally associated with the use of a medicinal (investigational) product, whether or not it is related to the medicinal (investigational) product. This includes an exacerbation of pre-existing conditions or events, intercurrent illnesses, drug interaction or the significant worsening of the indication under investigation that is not recorded elsewhere in the

CRF under specific efficacy assessments. Anticipated fluctuations of pre-existing conditions, including the disease under study that does not represent a clinically significant exacerbation or worsening need not be considered AEs.

It is the responsibility of the Investigator to document all AEs that occur during the study from the time the ICF is signed. AEs and SAEs should be followed until resolution or until the event is stable. An AE should be reported on the appropriate page of the CRF.

Each separate AE episode must be recorded. For example, if an AE resolves completely or resolves to baseline and then recurs or worsens again, this must be recorded as a separate AE. For AEs to be considered intermittent, the events must be of similar nature and severity.

Adverse Reaction Definition

An adverse reaction is any untoward and unintended response that is related to the administration of the IMP at any dose.

Onset Date, End Date

If an AE starts during the study but did not end before the final closing (follow-up) visit, the Investigator must make a reasonable effort to establish the outcome and the end date of the AE. If this is not possible (eg, because the AE is still ongoing) or the subject is lost to follow-up, there will be no end date for the AE.

For all AEs that resolve, resolve with sequelae, or have a fatal outcome, an end date must be provided.

If an AE stops and restarts later, all occurrences have to be recorded separately.

Assessment of Severity

Severity of AEs will be assessed by the Investigator using NCI CTCAE v5.0, 27 November 2017 ([CTCAE v5.0](#)). Grades of the NCI CTCAE refer to the severity of the AE as follows:

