- Grade 1 Mild; asymptomatic or mild symptoms; clinical or diagnostic observations only; intervention not indicated.
- Grade 2 Moderate; minimal, local or non-invasive intervention indicated; limiting age-appropriate instrumental Activities of Daily Living (ADL).
- Grade 3 Severe or medically significant but not immediately life-threatening; hospitalisation or prolongation of hospitalisation indicated; disabling; limiting self-care ADL.
- Grade 4 Life-threatening consequences; urgent intervention indicated.
- Grade 5 Death related to AE.

If there is a change in severity of an AE, every episode of the AE will be captured separately and all required information for every episode will be provided separately.

Assessment of Causality

Every effort will be made by the Investigator to assess the relationship of the AE, if any, to the IMP. Causality should be assessed using the categories presented in the following table:

Unrelated:	Clinical event with an incompatible time relationship to IMP administration, and that could be explained by underlying disease or other drugs or chemicals or is incontrovertibly not related to the IMP.
Unlikely:	Clinical event whose time relationship to IMP makes a causal connection improbable, but that could plausibly be explained by underlying disease or other drugs or chemicals.
Possibly:	Clinical event with a reasonable time relationship to IMP, but that could also be explained by concurrent disease or other drugs or chemicals.
Probably:	Clinical event with a reasonable time relationship to IMP, and is unlikely to be attributed to concurrent disease or other drugs or chemicals.
Definitely:	Clinical event with plausible time relationship to IMP, and that cannot be explained by concurrent disease or other drugs or chemicals.

Action Taken with IMP

The Investigator will describe the action taken in the appropriate section of the CRF, as follows:

- None (no action taken)
- Unknown
- IMP temporarily interrupted – only for Part B and Part C (date, time and reason to be provided)
- IMP permanently discontinued (date and reason to be provided)
- Other (to be specified)

Outcome of Adverse Event

The final outcome of the AE will be documented in the appropriate section of the eCRF, as follows:

- Recovered
- Recovered with Sequelae
- Ongoing
- Unknown
- Death

Follow-up of Adverse Events

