All Investigators should follow up subjects with AEs or SAEs until the event is resolved or until, in the opinion of the Investigator, the event is stabilised or determined to be chronic. Details of AE or SAE resolution must be documented in the CRF.

Subjects should be followed up to the last follow-up visit, (ie, Day 7 after receiving the last dose of IMP in Part A, Day 12 in Part B, and Day 34 in Part C) and any AEs that occur during this time should be reported according to the procedures outlined above.

For all SAEs, where important or relevant information is missing, active follow-up should be undertaken.

A follow-up report must be completed when an SAE resolves, is unlikely to change, or when additional information becomes available. In case the SAE is a suspected unexpected serious adverse reaction (SUSAR), follow-up information must be provided within the timelines as requested by Syneos Health Safety & Pharmacovigilance.

If new or amended information on a reported SAE becomes available, the Investigator can report this on a new SAE form using the completion guidelines. If using the original form to notify further information, all new or amended information need to be initialled and dated in order all changes are clearly identified.

Documentation and Reporting of Adverse Events

An AE should be reported and documented in accordance with the procedures outlined below. All AEs occurring during the study must be documented on the relevant CRF pages. The following data should be documented for each AE:

- Diagnosis, if not available, symptoms
- Classification of ‘serious’ or ‘not serious’
- Severity
- Date and time of first occurrence and date and time of resolution (if applicable)
- Action taken with the IMP
- Causal relationship
- Outcome of event (unknown, recovered, ongoing, recovered with sequelae, death [with date, time, and cause reported])

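### Protocol 8.4.4 allows a critically ill child who needs ventilation, PAP or high-flow oxygen to be withdrawn from the study, not only from drug, and nothing requires scheduled efficacy assessments to continue

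*Protocol*

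**What the plan says.** Protocol 8.4.4 gives a list of reasons for which a subject may be withdrawn from the study. One of them is "Becoming critically ill with respiratory insufficiency leading to the requirement for mechanical ventilation/positive airway pressure (PAP)/high-flow oxygen". The action named is leaving the study; stopping IMP alone is not mentioned there.

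Other sections bear on what happens next:

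- **Prohibited medication (8.5.6.2).** A child who starts a prohibited drug stops study treatment but "must remain in the study according to the post-study drug treatment period specified in the Schedule of Assessments".
- **Permitted medication (8.5.6.1).** Certain drugs, "e.g. in patients requiring procedures or ventilation, will be permitted", so the protocol foresees ventilated children on study.
- **Adverse events (10.1.3.1).** Permanent discontinuation of IMP is a separate action. "AEs and SAEs should be followed until resolution or until the event is stable", and "Subjects should be followed up to the last follow-up visit", which is Day 34 in Part C.
- **Early withdrawal (9.4.5, repeating 8.4.4).** "Parents/legal guardians who withdraw their child from the study will be encouraged to allow their child to complete the same final evaluations".
- **Replacement (8.4.5).** In Part C a child who has not completed at least 6 doses may be replaced.
- **Exclusion 3 (8.4.3).** Part C screens out only children likely to need imminent invasive ventilation, so PAP or high-flow oxygen after entry remains possible.
- **SAP v2.0.** Section 8.3 censors time to improvement and time to resolution at the last record of signs and symptoms. Section 10.2.1 calculates DAVG from the available swabs over the period they cover.

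**The concern.** The trigger is close to an efficacy outcome. Positive-pressure or high-flow support scores the maximum 3 points on item 2 of the clinician ReSVinet scale (Protocol 17.6), and oxygen use, time to improvement, time to resolution and composite severity are Part C secondary endpoints. If a site withdraws the child at that moment, the later efficacy data are missing because of how ill the child was.

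For the time-to-event endpoints, censoring at the last record treats a deteriorating child as having the same prospects as those still under observation. An arm that loses more such children would look better than it should. For DAVG, averaging over a short early period of a progressive decline gives a smaller decline, so the arm that loses more children would tend to look worse. Because the provision is optional, two sites may also handle the same clinical course differently.

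**Working it through.** **1. What can be lost (Protocol Table 3a).** Dose k is taken at 12(k−1) h, so the pre-Dose 3, 5 and 7 assessments fall at 24, 48 and 72 h. The counts are records lost if the child leaves straight after those assessments and no final evaluation is done.

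| Record | Scheduled at | 24 h | 48 h | 72 h |
|---|---|---|---|---|
| Signs and symptoms | Doses 2–10, Days 7, 14, 34 (12) | 10 | 8 | 6 |
| Clinician ReSVinet | Doses 3, 5, 7, 9, Days 7, 14, 34 (7) | 6 | 5 | 4 |
| Supplemental oxygen | Doses 1–10 (10) | 7 | 5 | 3 |
| Non-optional swabs to Day 7 | Doses 3, 5, 6, 7, 9, Day 7 (6) | 5 | 4 | 2 |

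These are upper limits. A final evaluation with the Day 7 content would recover one swab, one symptom record and one ReSVinet score.

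**2. The plan's own sample size (Protocol 11.2).** Difference 1.0 log10, SD 1.25, two-sided 0.05, power 90%. A two-sample t test needs 33.8 per group, so 34 (power 0.90). Adding 10%: 34 × 1.10 = 37.4, stated as 37. The figures reproduce.

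**3. Effect on DAVG.** Assumptions that are not in the documents: 1 to 3 children per arm withdrawn; linear viral decline; withdrawn children decline at the average rate; SD stays at 1.25. Planned means are −1.5 (placebo) and −2.5 (active, from the 1 log10 effect). The Day 7 visit is at most 48 h after Dose 10, so T = 108 + 48 = 156 h. Under linear decline a DAVG stopped at t is the fraction r = t/156 of the full value: 0.154, 0.308 and 0.462 at 24, 48 and 72 h. Under SAP 10.2.1 a withdrawn child with a post-baseline swab still counts, so n = 37 per arm. With w_P and w_A withdrawn:

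Difference = 2.5 × [1 − (w_A/37)(1 − r)] − 1.5 × [1 − (w_P/37)(1 − r)]

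Example, 24 h, one placebo and three active: 2.5 × (1 − 0.0686) − 1.5 × (1 − 0.0229) = 2.329 − 1.466 = 0.863.

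| Placebo/active withdrawn | 24 h | 48 h | 72 h |
|---|---|---|---|
| 1/1 | 0.977 | 0.981 | 0.985 |
| 3/3 | 0.931 | 0.944 | 0.956 |
| 3/1 | 1.046 | 1.037 | 1.029 |
| 1/3 | 0.863 | 0.888 | 0.913 |

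Power (two-sample t, n = 37 per arm, SD 1.25):

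- No loss, difference 1.00: 0.92.
- 3/3: 0.885, 0.893 and 0.901 at 24, 48 and 72 h.
- 1/3: 0.83, 0.85 and 0.87.

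**4. Slower clearance.** Suppose withdrawn children clear virus at half the average rate (48 h, 1/3). Full follow-up gives 2.5 × (1 − 0.5 × 3/37) − 1.5 × (1 − 0.5 × 1/37) = 0.919. Truncation gives 0.863. The shift due to stopping early is 0.056, against 1.00 − 0.888 = 0.112 with average decline.

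**5. Replacement.** Leaving at 24 or 48 h means 2 or 4 doses, so those children may be replaced. The Part C mITT in Protocol 11.1.1 needs only one dose and a centrally confirmed positive test, so a replaced child stays in the analysis and the dilution remains, while the added child raises n. The power figures leave this out.

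**6. Secondary clinical endpoints.** The documents give no escalation rate and no expected event times for the current Part C, so no effect can be calculated.

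**The case against.** The strongest reply is that 8.4.4 permits withdrawal and orders nothing. A site can stop IMP and keep the child on study, and 8.5.6.1 expects ventilated children there. Prohibited medication is on the same 8.4.4 list, yet 8.5.6.2 keeps those children in the study, so a listing does not by itself end assessments. That stands as far as it goes. But 8.5.6.2 supplies the missing instruction for prohibited medication, and no section supplies it for respiratory deterioration.

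The heading in 9.4.5 also covers discontinuation, so its final evaluations may reach these children. They are only encouraged, the text is addressed to parents who withdraw their child, and they do not replace the assessments in between.

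The SAP already has rules for early loss, and its DAVG rule does not depend on the older Part C design. That is right, and no new DAVG rule is needed. The rules use what was collected; they cannot recover what was not.

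A reader might infer three stronger things that the documents do not support:

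- That any use of PAP or high-flow oxygen triggers withdrawal. The listed reason requires the child to become critically ill with respiratory insufficiency.
- That the clinical event itself is lost. Adverse events are followed to resolution or stability.
- That the primary comparison is seriously underpowered or biased in a known direction. The 10% allowance already covers losses of this order, and the direction depends on which arm loses more children.

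**Conclusion.** The gap is real and modest. Protocol 8.4.4 lets a site end study participation on a severity outcome, and no text requires scheduled efficacy assessments to go on.

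For the primary DAVG the effect is probably small: a difference of 0.86 to 1.05 instead of 1.00. Power falls to 0.83 only if three active children and one placebo child leave at 24 h; with three in each arm it stays near the planned 90%. These figures rest on assumed withdrawal numbers, linear average decline, an unchanged SD and all 37 per arm analysed.

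The greater exposure is in the secondary clinical endpoints, through outcome-dependent censoring, and it cannot be sized. This is a worthwhile clarification, not a defect that threatens the trial's main conclusion.

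**What to change.** Add one sentence under the 8.4.4 list, modelled on 8.5.6.2: a child who becomes critically ill with respiratory insufficiency and needs ventilation, PAP or high-flow oxygen may stop IMP but remains in the study for the assessments already scheduled, where feasible, through the last visit (Day 34 in Part C), unless the parents withdraw consent.

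Optionally, in the Part C SAP update, which is needed anyway because SAP v2.0 still describes a 1:1 Part C with clinical primary endpoints, add a sensitivity analysis of time to improvement and time to resolution. In it, a child withdrawn at escalation counts as not improved and not resolved instead of being censored at that point. The main definitions stay as they are. Protocol 11.1 allows SAP amendments up to database lock and unblinding.

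The cost is one protocol sentence and, if wanted, one analysis; there are no new visits and no change in sample size. There are limits: swabs and signs such as retractions, grunting and room-air SpO2 are hard to collect or interpret in a ventilated infant, and Table 3a has no oxygen record after Dose 10, so later support status would come only from ReSVinet item 2.
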